5 STUDY TREATMENT(S)

5.1 Study Drug

Etrasimod is an investigational product and will be provided by the Sponsor for the study. Etrasimod will be supplied as 2 mg immediate release tablets, packaged in high-density polyethylene bottles with child-resistant screw caps. [REDACTED]

Bottles should be stored at [REDACTED] °C ([REDACTED] °F); excursions are permitted from [REDACTED] °C to [REDACTED] °C, until medication is dispensed.

5.2 Dosage, Administration and Accountability

Investigational product will be dispensed to the patients under the supervision of the investigator or his/her designee. Patients should be instructed to take their tablet **as a first thing** in the morning on an empty stomach. Patients should be advised not to crush, break, chew, or dissolve the tablet and to take study medication with water.

Investigational product will be dispensed as follows:

- 1 bottle of 40 tablets at Day 1. Patient will be requested to bring the bottle back for drug accountability on Week 2; patient will return the bottle with all remaining tablets at Week 4.
- 1 bottle of 40 tablets at Week 4. Patient will return the bottle with all remaining tablets at Week 8.
- 1 bottle of 40 tablets at Week 8. Patient will return the bottle with all remaining tablets at Week 12.

The investigator will maintain accurate records of the receipt of all study medication. In addition, accurate records will be kept regarding when and how much study medication is dispensed and used by each patient in the study.

Investigational product accountability will be performed by the site at Week 2, Week 4, Week 8 and Week 12.

Reasons for deviation from the expected dispensing regimen must also be recorded. Study medication will be reconciled by the Arena Pharmaceuticals monitor or contracted designee. The investigator agrees to provide sufficient access to study medication as required for the reconciliation process to be completed in a timely fashion.

5.3 Investigational Product Retention at Study Site

At completion of the study, all study medication will be reconciled by the Arena Pharmaceuticals monitor or contracted designee, and then returned at the direction of the Arena Pharmaceuticals to be retained or destroyed according to applicable country regulations. Prior to any action being taken with study medication after the study is completed, the investigator will contact Arena Pharmaceuticals (or contracted CRO) for approval of such action.

6 STUDY PROCEDURES

6.1 Informed Consent

Prior to undergoing any study specific procedures, each subject must sign a written Informed Consent Form (ICF) that has been approved by the investigator's designated Institutional Review Board (IRB) or Independent Ethics Committee (IEC) and by the Sponsor. All patients will be informed of the nature of the protocol and investigational therapy, their possible hazards, and their right to withdraw at any time, and will sign a form indicating their consent to participate prior to the initiation of study procedures. The signed ICF should be included in the patient's medical record, that should also contain written documentation indicating that informed consent was obtained. Study procedures will be conducted only after a written informed consent has been obtained and documented appropriately in the source data.

6.2 Medical History

A complete medical history will be collected at screening. Concomitant medications, recent illnesses, and participation in other investigational drug studies will also be recorded. The examinations will be performed as outlined in [REDACTED]

6.3 Physical, Ophthalmological and Neurological Examinations

6.3.1 Physical Examination

The examinations will be performed as outlined in [REDACTED]. The physical examination will be performed by the investigator. It will include assessments of general appearance, skin, head (eyes, ears, nose, and throat), neck, thyroid, lungs, heart, abdomen, back, lymph nodes, and extremities, and body weight. Height will only be obtained at screening.

6.3.2 Ophthalmological Examination

This examination will include visual acuity and dilated ophthalmoscopy (by an ophthalmologist) and with OCT (where available) to rule out and monitor for any significant retinal disease, including macular edema. Retinal photos will be taken. The examinations will be performed as outlined in [REDACTED]

6.3.3 Neurological Examination

[figure not shown]
The neurological examination includes assessments of the neurological system (cranial nerves, motor and sensory function, coordination, and mental status). The examinations will be performed as outlined in [REDACTED]. In addition, monitoring for PML, a potential AE of S1P₁ agonists, will be performed at each site visit [REDACTED] using a subjective PML checklist (refer Section [6.12.1.1](#)).

[figure not shown]
The investigator or sub-investigator will administer the subjective PML checklist during screening to exclude patients with positive responses from enrolling into the study. The

subjective PML checklist will also be administered at each site visit (except Day -1) to probe for symptoms suggestive of PML. Any patients reporting signs and/or symptoms of PML will undergo objective testing and must be referred to a neurologist for a full evaluation. Additional information on PML is provided in Section 6.12.1.1 and a copy of the PML checklist is provided in [Appendix 1](#).

6.4 Vital Signs

Supine (laying face upward) blood pressure, heart rate, temperature, and respiratory rate will be measured after the patient has been resting for 5 minutes. Vitals signs will be measured prior to any blood draw or any other invasive procedure that occurs at the same visit or time point. Vital signs will be measured according to the time points in the

6.6 Tuberculosis Screening

All patients will complete TB screening to determine eligibility. All patients must complete QuantiFERON[®] Test at screening.

Patients will be excluded from the study participation if they have active or latent TB, regardless of treatment history or a history of TB that has not been successfully treated. Patients will be also excluded from the study participation if they had a positive QuantiFERON[®] test or 2 successive indeterminate QuantiFERON[®] tests at screening.

█ █

█

6.8 Clinical Laboratory Tests

The clinical laboratory tests will be performed as outlined in █
█ Tests will be performed in the local laboratory as per study site standard. In the event of abnormal clinical laboratory values, the physician will make a judgment whether or not the abnormality is clinically significant. If clinically significant, it will be captured and recorded as an AE.

6.8.1 List of Laboratory Parameters

Laboratory tests will include the following:

Serum Chemistry

Albumin (ALB)
Alkaline phosphatase (ALK-P)
Alanine aminotransferase (ALT; SGPT)
Amylase
Aspartate aminotransferase (AST; SGOT)
Bicarbonate
Blood urea nitrogen (BUN)
Calcium (Ca)
Chloride (Cl)
Creatinine
Creatine kinase and MB subtype (if elevated) (% and total MB)
Gamma-glutamyl transferase (GGT)
FSH
Glucose
Lactate dehydrogenase (LDH)
Lipase
Magnesium
Phosphate
Potassium (K)
Sodium (Na)
Total bilirubin
Total cholesterol
Total protein
Triglycerides

Hematology

Hematocrit (Hct)
Hemoglobin (Hb)
Mean corpuscular hemoglobin (MCH)
Mean corpuscular volume (MCV)
Platelet count
Red blood cell count (RBC)
White blood cell count (WBC) with differential (% and absolute counts)

Coagulation

Prothrombin time (PT)
Activated partial thromboplastin time (PTT)
International Normalized Ratio (INR)

Additional tests

Serum human chorionic gonadotropin (hCG)
Follicle stimulating hormone (FSH)
HIV test
HBsAg
Anti- HCV
VZV IgG
QuantiFERON®

6.8.2 Virology

Evaluation of human immunodeficiency virus (HIV), hepatitis B (hepatitis B surface antigen), hepatitis C virus, and VZV IgG antibody will be performed at screening only.

6.8.3 Urinalysis

Urinalysis will follow the local practice at the study site (as dip-stick). Tests will be performed as outlined in [REDACTED]. Parameters for clinical laboratory tests include the following:

- appearance + color
- specific gravity
- pH
- leukocytes
- protein
- glucose
- nitrites
- ketones
- urobilinogen
- bilirubin
- blood/erythrocytes

Microscopic urinalysis will be performed when there is a positive or abnormal macroscopic urinalysis result as deemed necessary by the investigator.

6.8.4 Sample Collection

All blood and urine samples will be collected according to site standards. Tests will be performed as outlined in [REDACTED].

6.8.5 Blood Volume

Total blood volume collected for CBC is up to 200 mL during the study.

6.9 Efficacy Assessments

All efficacy assessments are treated as exploratory, this being a proof of concept study.

6.9.1 Patient Global Assessment for Active Skin Manifestation Visual Analog Scale (VAS)

The patient global assessment for active skin manifestation is a tool to capture the disease and pain severity using a visual analogue to mark the patient's score. The assessment sheet asks the patient to rate their disease severity from "not severe" to "extremely severe" and pain levels from "no pain at all" to "worst pain imaginable". This assessment sheet ([Appendix 3](#)) will be completed by the patient as per [REDACTED].

The assessment will be conducted at the study site during the patient's scheduled visits.

6.9.2 Physician Global Assessment for Active Skin Manifestations

The physician's global assessment for active skin manifestations will record the number of ulcers, target lesion noted for endpoint evaluation, diameters of each target lesion and score of evaluation at each visit. The scores range from 0 (total resolution) to 4 (no evidence of healing) ([Appendix 2](#)).

This assessment sheet will be completed by the investigator after evaluating the patient's disease as per [REDACTED]

6.9.3 Dermatology Life Quality Index (DLQI)

DLQI has been developed to use 10 simple questions to assess how much a patient's life is affected through their skin problems ([Appendix 4](#)). This assessment sheet will be completed by the patient as per [REDACTED]

6.9.4 C-reactive Protein (CRP)

Elevation of CRP concentration have been observed in active PG and during subsequent relapses. High CRP levels have been also associated with poor prognosis of PG. Therefore CRP will be measured during the study to monitor potential correlation between the response to therapy and disease activity^{29,30}.

6.10 Other Exploratory Assessments

The following exploratory measures will also be assessed as per [REDACTED]

6.10.1 Skin Punch Biopsies

Histology data will be collected from the lesions via punch biopsies. Skin punch biopsies will be taken only if possible or necessary if deemed by investigator.

6.10.2 Imaging

Digital photos of the **target lesion** will be taken to document visual changes in the lesion.

6.10.3 Surface Area Evaluation

Evaluation of the changes in surface area of the target lesion will be done by the investigator.

6.11 Hematologic Assessments

6.11.1 Complete Blood Count

Blood samples for complete blood count (CBC) with differential and platelet count will be assessed. Tests will be performed as outlined in [REDACTED]

If the absolute peripheral lymphocyte count has not recovered to at least 80% of the baseline value at the 2-week follow-up (week 14), the patient must return for weekly CBCs until the absolute peripheral lymphocyte count has returned to at least this value.

6.12 Adverse Events Assessments

Patients will be monitored from ICF signature to 2 weeks after the last dose of study drug for AEs to the study drug and/or procedures.

AEs will be recorded and reported in accordance with ICH GCP and 21 CFR§312.32. The definitions of AEs and serious AEs (SAEs) will be as given in the ICH Topic E2A, ICH Guideline “Note for Guidance on Clinical Safety Data Management: Definitions and Standards for Expedited Reporting.” The outcome of an AE will be defined according to ICH Topic E2B, ICH Guideline “Note for Guidance on Clinical Safety Data Management: Data Elements for Transmission of Individual Case Safety Reports.” The relationship to investigational product will be classified using the World Health Organization (WHO) criteria.

6.12.1 Adverse Event Reporting

Patients will be instructed to report all AEs, which can be reported at any time. AEs that occur from ICF signature until the time of administration of the first dose of etrasimod will be regarded as ‘pre-treatment’ and recorded as an AE. All events reported following study medication administration up to 30 days after the last medication intake will be presented as treatment emergent AEs (TEAEs).

Monitoring of ongoing AEs will be continued up to 2 weeks after study medication administration.

For this study, an AE is defined as: “Any untoward medical occurrence in a study patient administered etrasimod which does not necessarily have to have a causal relationship with this treatment.” An AE can therefore be any unfavorable and unintended sign (including an abnormal laboratory finding), symptom, or disease temporally associated with the use of the study medication, whether or not related to the product. AEs can be any of the following:

- Unfavorable changes in general condition
- Subjective or objective signs/symptoms
- Concomitant disease or accidents
- Clinically relevant adverse changes in laboratory parameters observed in a patient in the course of a clinical study
- Pre-existing conditions which worsen in severity or frequency or which have new signs/symptoms associated with them

Lymphopenia will not be captured as an AE because it is an expected pharmacologic effect of the drug.

AEs will be elicited at the time indicated in the schedule by asking the question: “Since you were last asked, have you felt unwell or different from usual in any way?” Any

adverse or unexpected events, signs and symptoms, will be fully recorded on the AE Form including details of intensity, onset, duration, outcome and relationship to the drug as determined by the PI. Whenever possible, a constellation of signs and symptoms should be recorded as a unifying diagnosis (e.g., self-limited fever, runny nose, cough, and scratchy throat should be captured as an upper respiratory infection rather than by the individual signs and symptoms). AEs may also be reported at any time. The type and duration of follow-up of patients after AEs will be documented.

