4 STUDY POPULATION

The study population will consist of eight (8) patients with PG who fulfill eligibility (inclusion & exclusion) criteria.

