6.12.3 Assessment of Adverse Event Severity

The severity of each AE will be assessed at onset by a nurse and/or physician. When recording the outcome of the AE the maximum severity of the AE experienced will also be recorded. The severity of the AE will be graded according to the CTCAE v4.03³² definitions, listed below:

Grade 1: Mild; asymptomatic or mild symptoms; clinical or diagnostic observations only; intervention not indicated.

Grade 2: Moderate; minimal, local or noninvasive intervention indicated; limiting age-appropriate instrumental Activities of Daily Living (ADL)*.

Grade 3: Severe or medically significant but not immediately life-threatening; hospitalization or prolongation of hospitalization indicated; disabling; limiting self-care ADL**.

Grade 4: Life-threatening consequences; urgent intervention indicated.

Grade 5: Death related to AE.

Activities of Daily Living:

*Instrumental ADL refer to preparing meals, shopping for groceries or clothes, using the telephone, managing money, etc.

**Self-care ADL refer to bathing, dressing and undressing, feeding self, using the toilet, taking medications, and not bedridden.

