7.2 Data Coding

7.2.1 Adverse Events

AEs will be coded using the most current Medical Dictionary for Regulatory Activities (MedDRA) and tabulated, including categorical information of interest such as onset and resolution times, time of onset relative to dose, severity at onset, maximum severity, causal relationship to study medication, and action taken. Whenever possible, a constellation of signs and symptoms should be recorded as a unifying diagnosis (e.g., self-limited fever, runny nose, cough, and scratchy throat should be captured as an upper respiratory infection rather than by the individual signs and symptoms). AEs will be regarded as 'pre-treatment' if they occur between screening and the time of administration of the first dose of etrasimod. All other AEs that occur after the first dose of study medication will be considered to be 'treatment-emergent'.

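### Sections 6.12.1 and 7.2.1 sort adverse events on different bases (when reported, when occurring), and the visible text does not say how a screening-period event that worsens after the first dose is classed

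*Combined protocol and SAP*

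**What the plan says.** Two sections of the protocol classify adverse events relative to the first dose.

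- **Section 6.12.1, pre-treatment:** "AEs that occur from ICF signature until the time of administration of the first dose of etrasimod will be regarded as" pre-treatment. The basis is occurrence, starting at consent.
- **Section 6.12.1, treatment-emergent (the next sentence):** "All events reported following study medication administration up to 30 days after the last medication intake will be presented as treatment emergent AEs". The basis is the report.
- **Section 7.2.1, pre-treatment:** events count as pre-treatment "if they occur between screening and the time of administration of the first dose of etrasimod". The basis is occurrence, starting at screening.
- **Section 7.2.1, treatment-emergent:** "All other AEs that occur after the first dose of study medication will be considered to be" treatment-emergent. The basis is occurrence.

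Two other places bear on worsening. The list of what counts as an AE in section 6.12.1 includes "Pre-existing conditions which worsen in severity or frequency or which have new signs/symptoms associated with them". Section 6.12.3 has severity graded at onset and adds: "When recording the outcome of the AE the maximum severity of the AE experienced will also be recorded". Section 7.2.1 plans to tabulate onset relative to dose, severity at onset and maximum severity.

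The contents list shows a section 8.7.1 on adverse events, but its text is not in the copy available. Section 8 also leaves analysis details to a separate SAP. Neither absence is held against the plan; it limits what can be concluded.

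**The concern.** Safety and tolerability is one of the trial's two objectives. There is no control group, so the timing of an event relative to the first dose is a main means of separating what happened on etrasimod from background illness. The rule that decides which events enter the TEAE table therefore has to give one answer for each event.

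Two things look wrong, and they pull in opposite directions. The reporting-based sentence can bring into the TEAE set an event that began before any drug was taken. The occurrence-based sentences can leave out an on-drug deterioration if the event first appeared in screening. When each rule ends is a separate matter and is not pursued here.

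**Working it through.** The plan gives no figure to reproduce, so the check applies each rule to the same events.

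**Case 1. Onset in screening, first reported after the first dose (for example at Week 2).**
- 6.12.1, pre-treatment sentence: pre-treatment.
- 6.12.1, TEAE sentence: treatment-emergent.
- 7.2.1: pre-treatment.

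The two sentences of 6.12.1 contradict each other, and the second contradicts 7.2.1. Followed literally, the TEAE sentence counts a pre-drug event as treatment-emergent.

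**Case 2. Onset and report both in screening; severity rises after the first dose; the site keeps one record.**
- 6.12.1 and 7.2.1: the event occurred before the first dose, so it is pre-treatment.

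Suppose the record holds Grade 1 at onset and Grade 3 as the maximum. A patient who reached Grade 3 before Day 1 and a patient who reached Grade 3 on drug then produce the same two grades. Unless the change is dated somewhere, no later analysis rule can tell them apart.

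**Case 3. As case 2, but the site enters the worsening as a new AE with its own onset.**
- 6.12.1 and 7.2.1: treatment-emergent.

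Cases 2 and 3 are the same clinical course. The class depends on a recording choice that the visible text does not settle.

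**Scale.** The number of patients is from section 4: "The study population will consist of eight (8) patients with PG who fulfill eligibility".
- One patient moved between classes: 1/8 = 12.5 percentage points in the affected row of the TEAE table.
- For context, with exact (Clopper-Pearson) 95% limits: 0/8 = 0% (0 to 36.9%); 1/8 = 12.5% (0.3 to 52.7%).
- Maximum screening share of study time, from section 3.2: 4 / (4 + 12 + 2) = 4/18 = 22.2%. With the 30-day TEAE window in place of the 2-week follow-up: 4 / (4 + 12 + 30/7) = 4/20.3 = 19.7%. These are shares of calendar time only.

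**The case against.** The strongest reply is that worsening is already covered. The AE definition in 6.12.1 includes worsening of pre-existing conditions, and a TEAE rule classifies whatever that definition produces, so it need not repeat it. This stands in part. A reader might infer that the plan ignores worsening altogether, and the documents do not support that: case 3 is a legitimate reading. What remains open is whether a condition that arises between consent and the first dose is pre-existing in the sense of that definition, and whether its worsening gets its own entry.

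A reader might also infer that section 6.12.3 requires one record per AE. It does not. It asks for onset severity and maximum severity, and neither demands nor forbids a new entry. The result in case 2 is therefore possible, not certain.

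Nor does the reporting-based sentence hide worsening. Its effect is to add pre-drug events to the TEAEs; the risk of leaving out deterioration comes from the occurrence-based sentences.

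It can further be said that little information is lost. Onset relative to dose is to be tabulated, so case 1 can be sorted out from the data, and with eight uncontrolled patients and no inferential comparisons individual cases can be read one by one. That is fair for case 1, where the repair is purely one of wording. It is less reassuring for case 2, where onset and maximum grade alone do not show when the maximum was reached.

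Finally, section 8.7.1 or the SAP may hold an operative definition. That could settle the analysis rule. It would not remove the contradiction between the sections that can be read, and it could not supply a date of worsening that sites were never asked to record.

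**Conclusion.** The point holds in two parts of different strength.

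1. The conflict between the reporting basis and the occurrence basis is certain from the text. It affects any event with onset before the first dose that is first reported afterwards. Treatment-emergence itself is set by occurrence only in 7.2.1; the other occurrence wording is the pre-treatment sentence of 6.12.1.
2. The handling of screening-period events that worsen on drug is unspecified in the visible text. Such an event can stay pre-treatment. This rests on the site keeping a single record without a dated severity change; the CRF, section 8.7.1 and the separate SAP could not be checked.

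One affected patient is worth 12.5 points in a row of the TEAE table. That carries over to overall TEAE incidence only if the patient has no other TEAE. A reader might take the 22% share of study time as a misclassification rate, but the documents do not support that. Only late-reported or worsening screening events are affected, and how many there will be cannot be estimated from the documents. The point deserves correction because it bears on a main objective of a small uncontrolled trial and costs little to put right.

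**What to change.** Use one definition in sections 6.12.1 and 7.2.1 and in the SAP: a TEAE is an AE with onset at or after the first dose, or with onset before the first dose and an increase in severity at or after it. In the TEAE sentence of 6.12.1, base the class on onset instead of on when the event is reported.

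Add an instruction that sites record the date of any post-dose increase in severity of an event that began before the first dose. A new AE entry or a dated severity change on the existing entry would both serve; the plan should name one. State also that this applies to events arising between consent and the first dose.

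The recording instruction has to be in place while data are being collected, since a SAP finalised before database lock cannot recover undated changes. The cost is a few sentences and a CRF completion instruction. TEAE counts may change slightly, in either direction: late-reported screening events drop out and worsening ones come in.

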6.12.2 Serious Adverse Events and Expedited Reporting of Adverse Events

An SAE is any untoward medical occurrence that at any dose results in the following outcomes:

- Death
- Is Life-Threatening
- Required/Prolonged Hospitalization
- Disability/Incapacity
- Congenital Anomaly/Birth Defect
- Important Medical Event

SAEs will be captured from the time of ICF signature to 30 days after the last dose of study drug, and will be monitored until resolution or stabilization.

An important medical event that may not result in death, be life-threatening, or require hospitalization may be considered a SAE when, based upon appropriate medical judgment, it may jeopardize the patient and may require medical or surgical intervention to prevent one of the outcomes listed in this definition. Examples of such a medical event includes allergic bronchospasm requiring intensive treatment in an emergency room or at

home, blood dyscrasias, or convulsions that do not result in in-patient hospitalization, or the development of drug dependency or drug abuse.

Elective hospitalization and/or surgery for clearly pre-existing conditions (for example a surgery that has been scheduled prior to the patient's entry into the study) will not be reported as a SAE. All other hospitalizations, including elective hospitalizations for any condition that was not pre-existing, will be reported as a SAE.

Any AE considered serious by the investigator or which meets SAE criteria must be reported to PPD Pharmacovigilance (PVG) within 24 hours from the time study site personnel first learn about the event.

The following contact information is to be used for SAE reporting:

EMEA ASIA Safety Central Mailbox: [REDACTED]
[REDACTED]

Or alternatively:

PPD Medical Affairs/Pharmacovigilance
PPD PVG Hotline: (United Kingdom number) [REDACTED]
PPD PVG Fax line: (United Kingdom number) [REDACTED]

A full description of every SAE will need to be provided to PPD PVG (this may be supported by source documentation such as laboratory reports or a discharge summary should the patient be hospitalized).

Other safety issues as defined in ICH Topic E2A, 21 code of federal regulations (CFR) §312.32, and EU Eudralex Volume 10 also qualify for expedited reporting. In these situations, the process will be as detailed for SAEs above:

- SAEs which could be associated with the trial procedures;

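### The unlimited exclusion of lymphopenia from AE capture in Section 6.12.1 conflicts with Sections 6.8 and 6.12.2, so serious or clinically significant cases may lack an AE or SAE record

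*Combined protocol and SAP*

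**What the plan says.** Section 6.12.1 makes a named exception to AE recording: "Lymphopenia will not be captured as an AE because it is an expected pharmacologic effect of the drug". It sets no upper limit and does not mention seriousness, clinical significance, cause or what was done with study drug.

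Three other statements point the other way:

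- Section 6.8, on abnormal laboratory values: "If clinically significant, it will be captured and recorded as an AE". Lymphocytes are not excepted.
- Section 6.12.1 itself, among the things that can be an AE: "Clinically relevant adverse changes in laboratory parameters observed in a patient in the course of a clinical study".
- Section 6.12.2: "An SAE is any untoward medical occurrence that at any dose results in the following outcomes". Its examples of an important medical event include "blood dyscrasias, or convulsions that do not result in in-patient hospitalization". Lymphopenia is not excepted here either.

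The reporting duty in Section 6.12.2 is worded from the AE: "Any AE considered serious by the investigator or which meets SAE criteria must be reported to PPD Pharmacovigilance (PVG) within 24 hours".

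Lymphocyte data are collected regardless. Section 6.8.1 lists the white-cell differential with absolute counts, and the synopsis names hematology as a safety assessment. Section 6.11.1 adds that, if the count is below 80% of baseline at Week 14, "the patient must return for weekly CBCs until the absolute peripheral lymphocyte count has returned to at least this value".

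**The concern.** That lymphopenia is expected is a good reason not to fill in an AE form for every on-target fall in count. It is not a reason to exempt a case that is serious, that the investigator judges clinically significant, or that is the recorded reason for stopping study drug. As worded, the exemption covers all of these.

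What is at stake is the record attached to the event. In this protocol severity grade (6.12.3), relationship to study drug (6.12.4), outcome (6.12.5) and action taken (6.12.6 and 6.12.7) are attributes of an AE, and Section 7.2.1 tabulates AEs by most of them. A laboratory count carries none of them except what can be graded from the number. Two oversight provisions also depend on AE records: an AE is a listed reason for withdrawal (6.14), and the incidence or severity of AEs is a listed ground for terminating the study (6.15). Safety and tolerability is one of the study's two objectives.

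**Working it through.** The plan states no figure on this point, so there is nothing to reproduce. The check is to apply each rule to the same case.

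| Case | Exemption in 6.12.1 | 6.8 and AE definition in 6.12.1 | 6.12.2 |
|---|---|---|---|
| Fall in count, not clinically significant | Not an AE | Not an AE | Not an SAE |
| Judged clinically significant, not serious | Not an AE | AE | Not an SAE |
| Meets a seriousness criterion | Not an AE | AE, if judged clinically significant | SAE by definition; reporting duty unclear |
| Recorded reason for interrupting or withdrawing drug | Not an AE | AE, if judged clinically significant | Depends on seriousness |

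1. In the first row the rules agree, and the exemption does what its stated reason supports.
2. In the second row they conflict directly. Reading the specific exception as overriding the general laboratory rule would settle this, but no text says so.
3. In the third row that reading does not help. The SAE definition stands on its own and would capture the event. The 24-hour duty, however, begins from an AE, and 6.12.1 says that lymphopenia is not captured as one. A site could reasonably conclude either that it must report or that the duty is never triggered.
4. In the fourth row, Section 6.14 offers an AE or the investigator's judgment as reasons for withdrawal. With the AE route closed, the stop would be recorded under another reason.

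**Illustration of size.** The inputs are n = 8 (Section 4) and an assumed number of serious cases, because the documents give no rate.

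- If 1 of 8 treated patients had serious lymphopenia and the exemption was followed, the AE table would show 0/8 instead of 1/8 = 12.5% (exact 95% CI 0.3% to 52.7%).
- If 2 of 8, it would show 0/8 instead of 2/8 = 25.0% (3.2% to 65.1%).

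The chance that at least one such case occurs is 1 − (1 − p)^8 for an assumed true rate p:

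| p | 1 − (1 − p)^8 |
|---|---|
| 2% | 14.9% |
| 5% | 33.7% |
| 10% | 57.0% |
| 20% | 83.2% |

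These rates are assumptions that show a range, not estimates. No interval should be put around a zero that a recording rule produces, since it would estimate nothing.

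**The case against.** The best case for leaving the text alone has four parts.

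**The data are not lost.** Differential counts are collected as safety data and incomplete recovery is followed weekly. This stands. A reader might infer that lymphopenia would vanish from the safety results, and the documents do not support that. Only the AE or SAE record is at risk.

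**Section 6.12.2 already captures serious cases.** It defines an SAE independently of the AE exemption, and Section 6.12 ties definitions and reporting to ICH E2A and 21 CFR 312.32. This stands in part. It rules out saying that expedited reporting is blocked, but it does not remove the ambiguity from a duty that starts with an AE. The blood dyscrasia example is also generic and depends on medical judgment; it does not name lymphopenia.

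**The specific rule overrides the general one.** This is an ordinary reading and is adequate for routine on-target falls. It does not settle the serious cases.

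**The clinical consequences stay reportable.** The exemption names lymphopenia only. Infections are still AEs, and significant infection has its own provision in Section 6.14. This stands. The documents present lymphocyte reduction as the intended mechanism and never call it the main risk of the drug. Nor does the visible text contain a stopping rule based on lymphocyte count, so the point about stopping drug rests only on investigator discretion and on the interruption and withdrawal categories in 6.12.7.

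One further limit applies. Section 8.7.5 on laboratory values appears in the table of contents, but its body is not in the text available for this review, and Section 8 promises a separate SAP. It cannot be said that a lymphocyte summary is missing.

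**Conclusion.** The conflict is real and rests on the wording alone. Section 6.12.1 excludes lymphopenia without limit; Section 6.8, the AE definition in 6.12.1 and the SAE definition in 6.12.2 make no such exception; and no text sets an order of precedence. Serious or clinically significant lymphopenia may be absent from the AE and SAE tables and from expedited reports, or be recorded at one center and not at another. It is not certain to be absent, because 6.12.2 read alone would capture serious cases.

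The size cannot be estimated from the documents. In 8 patients each affected case is 12.5 percentage points, and whether any occurs depends on a rate that is not given. The conclusion assumes that sites apply the exemption as written and that no redacted or separate text settles precedence. It should be corrected because the remedy is trivial and a lost SAE record is hard to rebuild afterwards, but it does not undermine the study's laboratory safety data.

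**What to change.** Reconcile Sections 6.8, 6.12.1 and 6.12.2 with one recording sentence in 6.12.1, for example: *An on-target fall in lymphocyte count alone is not recorded as an AE; lymphopenia that the investigator judges clinically significant, that meets a seriousness criterion, or that is recorded as the reason for interrupting or withdrawing study drug is recorded and reported under Sections 6.8 and 6.12.2.*

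If Section 8.7.5 or the SAP does not already do so, summarise from the CBC data already collected: lymphocyte count as a percentage of baseline and CTCAE grade by visit, the nadir, and the number of patients below 80% of baseline at Week 14.

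The cost is one sentence, possibly one table, and a few more AE forms. The change affects recording only: no tests are added, and no dose or clinical rule changes.
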